## 5.2. Dose Limiting Toxicities

All toxicities will be graded according to the NCI CTCAE version 4.0 and assessed for relationship to study medications.

The incidence of DLT(s) assessed in the first 6 evaluable subjects during the first 6 weeks will be to initially determine whether the dose level of combination therapy is tolerable. A subject will be considered evaluable for DLT if they have received at least 1 dose of pembrolizumab after receiving the initial week of azacitidine. DLT should not be an AE considered by the investigator to be disease related. The following drug-related AE (whether related to one or both agents) will be considered a DLT:

- Any Grade  $\geq 3$  drug-related non-hematological AE, including the following laboratory abnormalities
  - If a subject has baseline Grade  $\leq 1$  AST, ALT, or total bilirubin, a drug-related Grade  $\geq 3$  toxicity will be considered a DLT
  - If a subject has baseline asymptomatic Grade 2 AST or ALT due to tumor infiltration in the liver, drug-related elevations in AST and/or ALT  $> 2x$  baseline or a maximum of  $> 8x$  ULN that does not resolve to Grade 2 or less within 48 hours (if symptomatic) or that does not resolve to Grade 1 or less within 3 weeks of onset (if asymptomatic) will be considered a DLT.
- Any Grade  $\geq 3$  drug-related non-hematological laboratory abnormality with the following exceptions:
  - Grade 3 abnormal laboratory result that is asymptomatic and lasts no longer than 72 hours.
  - Grade 4 lymphocytopenia not associated with symptoms or clinical manifestations
- Any toxicity managed by discontinuation of pembrolizumab (see [section 9.1](#)).
- Any toxicity managed by discontinuation of azacitidine (see [section 9.2](#)).
- Grade  $\geq 3$  thrombocytopenia with bleeding, and febrile neutropenia of any Grade.

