### 1.1. Trial Design Overview

This is a single-arm, single-center, open-label trial of azacitidine combined with pembrolizumab in subjects with locally-advanced or metastatic pancreatic adenocarcinoma. Thirty-one evaluable subjects will be enrolled to assess the efficacy and safety of combination therapy in the second- line setting.

All subjects will have received systemic first-line chemotherapy, 5-FU or gemcitabine-based combination or monotherapy, prior to enrollment on the study. Azacitidine daily for 5 days will be given every 4 weeks (28 days). Fixed-dose pembrolizumab will be administered every 3 weeks for up to approximately 2 years beginning 2 weeks after initiation of azacitidine. The primary efficacy endpoint will be progression-free survival among all enrolled subjects. Disease progression will be determined based on RECIST 1.1 criteria; however, patients will be permitted to continue therapy following the development of progression of disease by RECIST 1.1 criteria if considered clinically appropriate by the study principal investigator.

As preliminary data suggests there is minimal toxicity overlap between pembrolizumab and a hypomethylating agent, there will be an accelerated Phase 1 dose determination component of the study. In the initial cohort, low-dose azacitidine will be administered, as studied in patients with advanced or metastatic solid tumors, and pembrolizumab will be administered at fixed dose

as detailed in the protocol. An initial cohort of 6 subjects will be enrolled, treated with combination therapy, and assessed for safety. Following enrollment of the initial 6 evaluable subjects all toxicity data will be reviewed. If 2 or more patients experience a treatment related dose-limiting toxicity (DLT) within the first 6 weeks of treatment administration (Defined in Section 5.2), then accrual at that dose level will stop. We will allow for 1 dose reduction in azacitidine and if agreed by the PI, the study will resume at the lower dose (Dose -1) and will again accrue 6 subjects who will receive combination therapy. If 2 or more subjects experience treatment related DLTs at this level, we will discontinue the combination study.

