If the combination dose is deemed safe ( $\leq 1$  DLT), the study will complete accrual with treatment of an additional 25 subjects at the safe combination dose. Adverse events will be monitored throughout the trial and graded in severity according to the guidelines in the NCI Common Terminology Criteria for Adverse Events (CTCAE) version 4.0. DLT is defined as a grade 3 or above toxicity according to the CTCAE version 4.0.

After the end of treatment, each subject will be followed by 30 days for adverse event monitoring. Serious adverse events and Events of Clinical Interest (ECI) will be collected for 90 days after the end of treatment or 30 days after the end of treatment if the subject initiates new anticancer therapy, whichever is earlier. Subjects who discontinue treatment for reasons other than disease recurrence will have post-treatment follow-up for disease status until disease recurrence, withdrawing consent, or becoming lost to follow-up. All subjects will be contacted by telephone every 3 months for overall survival until death, withdrawal of consent or the end of the study, whichever comes first.

[figure not shown]
Every subject enrolled will be required to have pre-treatment, biopsy-confirmed disease. Development of a predictive diagnostic assay that enables prospective identification of patients who are likely to respond to azacitidine plus pembrolizumab may allow for preselection of patients likely to benefit from treatment with these regimens in future clinical studies. To facilitate additional PD analysis, on-treatment biopsies will be required for all subjects after 8 weeks of therapy if felt to be clinically feasible by the treating physician. Tumor samples will be collected and analyzed for molecular changes that occur during treatment with azacitidine and pembrolizumab. These analyses will help elucidate early mechanisms of action, predictors of treatment response, and predictors of survival in pancreatic cancer. Changes in tumor-infiltrating T-cell activity, measured by expression of granzyme B and other exploratory makers, will be explored in freshly obtained tumor tissue prior to and during induction and maintenance treatment.

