### **13.1.1 Definitions of evaluable subjects**

Evaluable for toxicity: All patients will be evaluable for toxicity from the time of their first treatment with azacitidine.

Evaluable for DLT assessment: The initial 6 subjects treated with at least 1 cycles (5 doses) of azacitidine and 1 dose of pembrolizumab will be evaluated for DLT. Subjects who do not complete these doses will be replaced.

Evaluable for PFS- primary outcome: All subjects who receive a single dose of pembrolizumab will be included in the primary outcome analysis of PFS. If subjects are removed from study prior to completing a single dose of pembrolizumab, they will be replaced.

Evaluable for objective response: Only those patients who have measurable disease present at baseline, have received at least one cycle of therapy, and have had their disease re-evaluated will be considered evaluable for response. These patients will have their response classified according to the definitions stated below. (Note: Patients who exhibit objective disease progression prior to the end of cycle 1 will also be considered evaluable.)

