### **15.2. Populations for Statistical Analysis and Reporting**

#### **15.2.1 DLT Evaluable Population**

The DLT Evaluable Population consists of subjects in the initial 6 patient DLT cohort who complete at least 5 doses of azacitidine and 1 dose of pembrolizumab and completed the DLT observation period (6 weeks), and those who did not complete the DLT observation period and discontinued from study treatment due to a DLT event. The DLT Evaluable Population will be used for DLT assessments.

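### A run-in subject who leaves before week 6 without a DLT counts as DLT-free under 5.2 and 13.1.1 but is excluded under 15.2.1, and no section says whether that subject is replaced

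*Combined protocol and SAP*

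**What the plan says.** **The gate.** Section 1.1 stops accrual at a dose level on this condition: "If 2 or more patients experience a treatment related dose-limiting toxicity (DLT) within the first 6 weeks of treatment administration". On timing it says: "Following enrollment of the initial 6 evaluable subjects all toxicity data will be reviewed". With at most one DLT, "the study will complete accrual with treatment of an additional 25 subjects at the safe combination dose". Section 5.2 describes the same count: "The incidence of DLT(s) assessed in the first 6 evaluable subjects during the first 6 weeks".

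**Who counts, by dosing alone.** Section 5.2 makes a subject "evaluable for DLT if they have received at least 1 dose of pembrolizumab after receiving the initial week of azacitidine". Section 13.1.1 asks for five azacitidine doses and one pembrolizumab dose, then adds: "Subjects who do not complete these doses will be replaced". Section 5.3 replaces unevaluable patients and refers to 13.1.1 for who they are. Table 3 starts pembrolizumab in week 3.

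**Who counts, by dosing and observation.** Section 15.2.1 draws its set from the initial six-patient cohort. It takes those with the same minimum dosing "and completed the DLT observation period (6 weeks"). A subject who did not complete the period is kept only if a DLT ended treatment. The section names this set as the one for DLT assessment.

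**Follow-up after stopping.** Sections 5.1 and 10.6 carry adverse event reporting to 30 days after treatment ends.

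**The concern.** The limit of 2 DLTs is set for six subjects, each watched for 6 weeks. The plan defines the six in two incompatible ways, and they differ for the subject who receives the minimum doses and then leaves early without a DLT.

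Under 5.2 and 13.1.1 that subject stays among the six and an incomplete window is scored as DLT-free. Under 15.2.1 the subject drops out of both numerator and denominator, and the limit of 2 may be read on five or fewer.

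These are different faults, but both make it easier to clear a dose level. Clearing it commits 25 more subjects, and the gate is the only numerical toxicity rule in the protocol.

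**Working it through.** The plan states no target DLT rate and no pass probability for the gate, so there is no figure of its own to reproduce. DLT rates and leaving rates below are assumptions.

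**Step 1. One subject through each section.** The subject has five azacitidine doses and one pembrolizumab dose, and leaves on day 16 without a DLT.

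| Section | Treatment of this subject |
|---|---|
| 5.2 | Evaluable, DLT-free |
| 13.1.1 | Evaluable, DLT-free; not replaced, because the doses were completed |
| 5.3 | Not replaced, because it follows 13.1.1 |
| 15.2.1 | Excluded; nothing said on replacement |

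**Step 2. How much of the window can be lost.** The window is 6 × 7 = 42 days and pembrolizumab starts about day 15. A subject lost to all observation on day 16 contributes 16/42 = 38% of it. A subject who stops treatment but stays in contact is followed to about day 15 + 30 = 45, past day 42. That subject still misses the azacitidine course in week 5 and the pembrolizumab dose in week 6.

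**Step 3. Chance of clearing the dose.** With n full windows and true DLT rate p, P(0 or 1 DLT) = (1−p)^n + n·p·(1−p)^(n−1). At p = 1/3:

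- n = 6: 0.088 + 0.263 = 0.351
- n = 5: 0.132 + 0.329 = 0.461
- n = 4: 0.198 + 0.395 = 0.593

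| True DLT rate | Six windows | Five | Four |
|---|---|---|---|
| 10% | 0.886 | 0.919 | 0.948 |
| 20% | 0.655 | 0.737 | 0.819 |
| 30% | 0.420 | 0.528 | 0.652 |
| 1/3 | 0.351 | 0.461 | 0.593 |
| 40% | 0.233 | 0.337 | 0.475 |
| 50% | 0.109 | 0.188 | 0.313 |

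Under 15.2.1 without topping up, the five- and four-subject columns apply directly if leaving is unrelated to DLT risk. Under 5.2 and 13.1.1 they are ceilings, because they give the leaver no chance of a DLT.

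**Step 4. A leaver who carried part of the risk (5.2 and 13.1.1).** If one leaver has DLT probability f·p, P(clear) = P5 − f·(P5 − P6), where P5 and P6 are the values for five and six windows. At p = 1/3 with f = 0.38 (risk proportional to time, an assumption): 0.461 − 0.38 × (0.461 − 0.351) = 0.419.

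**Step 5. Averaged over an assumed leaving rate q (5.2 and 13.1.1).** The DLT count is Binomial(6, p·[1 − q(1−f)]). At p = 1/3:

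- q = 10%: 0.42 with f = 0, 0.39 with f = 0.38
- q = 20%: 0.49 with f = 0, 0.44 with f = 0.38

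The chance of at least one leaver among six is 1 − (1−q)^6, which is 47% at q = 10% and 74% at q = 20%.

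**The case against.** The strongest reply is that the window is mostly protected. Section 10.6 requires all adverse events to be reported for 30 days after treatment stops, which reaches about day 45. Serious events are collected for 30 days even when new therapy starts. Drug-related Grade 3 or higher non-hematological events, with listed laboratory exceptions, and toxicities managed by stopping either drug are DLTs under 5.2, so those who leave for toxicity are generally caught. All toxicity data are reviewed at the gate, the DSMC monitors every treated subject, and 13.8 allows termination for aggregate toxicity.

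Most of this stands, and it narrows the loss to death unrelated to drug, withdrawn consent, loss to follow-up, and missed second doses. It does not settle which definition governs, and 15.2.1 does not say whether off-treatment follow-up completes the period.

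Three stronger readings are tempting, and the documents do not support them.

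- A reader might infer that 15.2.1 drops the leaver with no replacement. That is a silence, not a stated rule. The references in 1.1 and 5.2 to six evaluable subjects, read with the 15.2.1 definition, could imply topping up. Against that, 5.2 has its own definition, which this subject meets.
- A reader might infer that both readings score unobserved time as tolerated. Only 5.2 and 13.1.1 do. Under 15.2.1 the fault is an unchanged limit on fewer subjects.
- A reader might take the 2-month median PFS as a guide to leaving: an exponential curve gives 1 − 2^(−27/60.9) = 26% with an event between days 15 and 42. That is not a leaving rate. The first scheduled on-study scan is at week 8, and 5.1 and 13.5 allow treatment beyond progression.

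**Conclusion.** The point holds as a contradiction in a decision rule. Sections 5.2 and 13.1.1 include a subject whom 15.2.1 excludes, and no replacement rule reaches that subject. Both readings favour clearing the dose.

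At a true DLT rate of 1/3, one such leaver raises the chance of clearing from 35% to at most 46%, a gain of 11 percentage points. If the leaver is counted and carried 38% of the risk, it is about 42%, a gain of 7 points. The effect is nil if nobody leaves early. It is small for subjects who stay in contact, apart from their missed second doses. The size rests on the assumed DLT rate and risk share, and on exits unrelated to DLT risk. How often it would arise cannot be judged from the documents.

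**What to change.** Reconcile 5.2, 5.3, 13.1.1 and 15.2.1 to one definition, using the plan's own 15.2.1 criterion:

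- A subject without a DLT counts toward the six only after the required doses and the full 6-week observation.
- State whether adverse event follow-up after stopping treatment counts as observation.
- Extend the replacement rule to subjects who leave earlier without a DLT, and keep them in the safety and PFS sets.

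The number of DLTs, the window and the DLT criteria are unchanged.

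The cost is wording in four sections and possibly a longer run-in. If the first dose level is cleared, replaced subjects who received pembrolizumab still count among the 31 for PFS, so the total need not rise. If it is not cleared, the maximum of 37 (6 + 31) in 6.4 and 15.4 rises by the number replaced: one replacement makes 38. Both sections should say so. The change should be made before the first six are read, because the choice of definition afterwards would be made with the DLT count known.

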### **5.3. Number of Patients**

Thirty-one subjects who are evaluable for progression-free survival will be enrolled. Unevaluable patients (as defined in [Section 13.1.1](#)) will be replaced.

## **6. SUBJECT SELECTION AND WITHDRAWAL**

Male and female subjects with advanced pancreatic ductal adenocarcinoma after progression on first-line systemic therapy who are considered incurable will be enrolled in this trial.

### **6.1. Inclusion Criteria**

In order to be eligible for participation in this trial, the subject must:

1. Be willing and able to provide written informed consent for the trial. In cases of partial impairment, impairment that fluctuates over time, or complete impairment due to dementia, stroke, traumatic brain injury, developmental disorders (including mentally disabled persons), serious mental illness, and delirium, a subject may be enrolled if the subject's legally authorized representative consents on the subject's behalf.
  - Age  $\geq$ 18 years of age on day of signing informed consent.
  - Have histologically or cytologically confirmed diagnosis of pancreatic ductal adenocarcinoma
  - Have a predicted life expectancy of greater than 3 months.
  - Have measurable disease based on RECIST 1.1.
  - Have a performance status of 0 or 1 using the ECOG Performance Scale within 3 days of first dose of study drug.
  - Have documented radiographic progression to or documented intolerance of first line systemic chemotherapy which included at least gemcitabine or 5-FU based regimen (including capecitabine).
  - Subjects who have documented disease recurrence within 6 months of completing neoadjuvant or adjuvant chemotherapy for limited disease will be eligible for study provided they have not received an additional line of systemic therapy. Subjects who recur greater than 6 months after completing adjuvant or neoadjuvant chemotherapy will not be eligible unless they receive additional chemotherapy for advanced disease.
  - Have a negative urine or serum pregnancy test within 72 hours prior to receiving the first dose of study medication (Cycle 1, Day 1) (female subjects of childbearing potential). If the urine test is positive or cannot be confirmed as negative, a serum pregnancy test will be required.
  - Be willing to use an adequate method of contraception for the course of the study through 120 days after the last dose of study medication (male and female subjects of childbearing potential [see [Section 8.5.2](#)]).

- Demonstrate adequate organ function as defined in Table 1.

**Table 1. Adequate Organ Function Laboratory Values**

System	Laboratory Value
Hematological	
Leukocytes	$\geq 2,000/\text{mcL}$
Absolute neutrophil count (ANC)	$\geq 1,500/\text{mcL}$
Platelets	$\geq 100,000/\text{mcL}$
Hemoglobin	$\geq 9\text{ g/dL}$ without transfusion or EPO dependency within 7 days
Renal	
Creatinine OR Measured or calculated a creatinine clearance (GFR can also be used in place of creatinine or CrCl)	$\leq 1.5 \times$ upper limit of normal (ULN) OR $\geq 60\text{ mL/min}$ for subject with creatinine levels $> 1.5 \times$ institutional ULN
Hepatic	
Total bilirubin	$\leq 2\text{ mg/dL}$ or direct bilirubin $\leq$ ULN for those with total bilirubin $> 2 \times$ ULN Subjects with Gilbert Syndrome will be eligible if total bilirubin is $< 3.0\text{ mg/dL}$ .
AST (SGOT) and ALT (SGPT)	$\leq 2.5 \times$ ULN OR $\leq 5 \times$ ULN for subjects with liver metastases
Albumin	$> 3.0\text{ mg/dL}$
Amylase and Lipase	$\leq 1.5 \times$ ULN. Subjects with Amylase or Lipase $> 1.5 \times$ ULN may enroll if there are neither clinical nor radiographic signs of pancreatitis
Coagulation	
INR or PT aPTT	$\leq 1.5 \times$ ULN unless subject is receiving anticoagulant therapy as long as PT or aPTT is within therapeutic range of intended use of anticoagulants

## 6.2. Exclusion Criteria

**The subject must be excluded from participating in the trial if the subject:**

- Is currently participating and receiving study therapy or has participated in a study of an investigational agent and received study therapy, or herbal/complementary oral or IV medicine within 2 weeks of the first dose of treatment.
- All toxicities attributed to prior anti-cancer therapy other than alopecia and fatigue must have resolved to Grade 1 (NCI-CTCAE Version 4.0) or baseline prior to administration of first dose of study drug. Subjects with toxicities attributed to prior anti-cancer therapy that are not expected to resolve and result in long-lasting sequelae, such as chronic neuropathy after platinum based therapy, are permitted to enroll
- Has received chemotherapy or radiotherapy within 14 days of first dose of study medication.
- Had a solid organ or hematologic transplant.

- Has experienced weight loss >10% over 2 months prior to first dose of study therapy.
- Has active autoimmune disease that has required systemic treatment in past 2 years (i.e. with use of disease-modifying agents, corticosteroids, or immunosuppressive drugs). Replacement therapy (e.g. thyroxine, insulin, or physiologic corticosteroid replacement therapy for adrenal or pituitary insufficiency, etc.) is not considered a form of systemic treatment.
- Has a diagnosis of immunodeficiency or is receiving systemic steroid therapy (at a dose greater than 10mg/day of Prednisone equivalent) or any other form of immunosuppressive therapy within 7 days prior to the first dose of trial treatment.
- Has a diagnosed additional malignancy within 2 years prior to first dose of trial treatment with the exception of curatively treated basal cell carcinoma of the skin, squamous cell carcinoma of the skin or curatively resected in situ breast cancers. Subjects with another malignancy diagnosed >2 years prior to the first dose of trial medication who were treated with curative intent and are not undergoing active therapy will be eligible.
- Has a known history of, or any evidence of, interstitial lung disease or active non- infectious pneumonitis.
- Has an active infection requiring systemic therapy.
- Has clinically relevant ascites at baseline (defined as requiring paracentesis) or with moderate radiographic ascites. A minimal amount of radiographic ascites is allowed.
- Has a history of current evidence of any condition, therapy, or laboratory abnormality that might confound the results of the trial, interfere with the subject's participation for the full duration of the trial, or is not in the best interest of the subject to participate, in the opinion of the treating investigator, including dialysis.
- Has known psychiatric or substance abuse disorders that would interfere with cooperation with the requirements of the trial.
- Is pregnant or breastfeeding, or expecting to conceive or father children within the projected duration of the trial, starting with the screening visit through 120 days after the last dose of trial treatment.
- Has received prior therapy with anti-PD-1, anti-PD-L1, or anti-PD-L2 agents, or if the subject has previously participated in Merck pembrolizumab clinical trials.
- Has a known history of human immunodeficiency virus (HIV) (HIV 1/2 antibodies).
- Has known chronic or acute Hepatitis B (e.g., HBsAg reactive) or Hepatitis C infection (e.g., HCV RNA [qualitative] is detected).
- Note: To qualify for enrollment, antiviral therapy for HBV must be given for at least 3 months, and HBV viral load must be less than 100 IU/mL prior to first dose of study

drug. Those on active HBV therapy with viral loads under 100 IU/mL should stay on

the same therapy throughout trial treatment. Those subjects who are anti-HBc (+), and negative for HBsAg, and negative for anti-HBs, and have an HBV viral load under 100 IU/mL do not require HBV anti-viral prophylaxis, but need close monitoring.

- Has dual infection with HBV/HCV or other hepatitis combinations at study entry.
- Has received a live vaccine within 30 days of planned start of study therapy (Cycle 1, Day 1).
- Note: The killed virus vaccines used for seasonal influenza vaccines for injection are allowed; however intranasal influenza vaccines (e.g., FluMist®) are live attenuated vaccines and are not allowed.

